8.3.5 Time Period and Frequency for Event Assessment and Follow-Up

Safety will be assessed by monitoring and recording potential adverse effects using the CTCAE at each study visit. Participants will be monitored by medical histories, physical examinations. If CTCAE grading does not exist for an adverse event, the severity of mild, moderate, severe, life-threatening, and death, corresponding to Grades 1-5, will be used whenever possible.

At each contact with the subject, the investigator will seek information on adverse events by non-directive questioning and, as appropriate, by examination. Adverse events may also be detected when they are volunteered by the subject during the screening process or between visits, or through physical examination, laboratory test, or other assessments. Information on all adverse events will be recorded in the source documentation. To the extent possible, adverse events will be recorded as a diagnosis and symptoms used to make the diagnosis recorded within the diagnosis event.

As much as possible, each adverse event or follow-up information will be evaluated to determine:

1. Severity grade (CTCAE Grade 1-5)
2. Duration (start and end dates)
3. Relationship to the study treatment or process – [Reasonable possibility that AE is related: No (unrelated/ not suspected) or Yes (a suspected adverse reaction)]. If yes (suspected) - is the event possibly, probably or definitely related to the investigational treatment?
4. Expectedness to study treatment or process – [Unexpected – if the event severity and/or frequency is not described in the investigator brochure or protocol].
5. Action taken with respect to study or investigational treatment or process (none, dose adjusted, temporarily interrupted, permanently discontinued, unknown, not applicable)
6. Whether medication or therapy taken (no concomitant medication/non-drug therapy, concomitant medication/non-drug therapy)
7. Whether the event is serious

Once an adverse event is detected, it should be followed until its resolution or until it is judged to be permanent, and assessment should be made at each visit (or more frequently, if necessary) of any changes in severity, the suspected relationship to the study treatment, the interventions required to treat it, and the outcome.

8.3.6 Adverse Event Reporting

Reporting Period

Adverse events will be reported from the time of informed consent until study completion.

Investigator Reporting: Notifying the Study Sponsor

N/A

Investigator Reporting: Local Reporting Requirements

The investigator will report AEs and SAEs to the IRB/EC of record and other local regulatory groups per the local requirements.

New information regarding the SAE will be reported as it becomes available and in the same manner that the initial SAE (i.e. SAE form). The investigator will follow the event to resolution or until the event is deemed and documented irreversible, whichever is longer.

8.3.7 *Serious Adverse Event Reporting*

The study investigator shall complete an Unanticipated Adverse Device Effect Form and submit to the reviewing Institutional Review Board (IRB) . The study investigator is responsible for conducting an evaluation of an unanticipated adverse device effect and shall report the results of such evaluation to the Food and Drug Administration (FDA) and to all reviewing IRBs and participating investigators per the applicable regulation.

8.3.8 *Reporting Events to Participants*

N/A

8.3.9 *Events of Special Interest*

N/A

8.3.10 *Reporting of Pregnancy*

Pregnancy, in and of itself, is not regarded as an AE unless there is suspicion that study device or process may have interfered with the effectiveness of a contraceptive medication or method. When a pregnancy has been confirmed in a subject, and the fetus is exposed to study device and/or process (maternally or paternally), the following procedures should be followed to ensure subject safety:

Data on fetal outcome are collected for regulatory reporting and device safety evaluation. Follow-up should be conducted for each pregnancy to determine outcome, including spontaneous or voluntary termination, details of the birth, and the presence or absence of any birth defects, congenital abnormalities, or maternal and/or newborn complications.

8.4 *Unanticipated Problems*

8.4.1 *Definition of Unanticipated Problems (UP)*

The Office for Human Research Protections (OHRP) considers unanticipated problems involving risks to participants or others to include, in general, any incident, experience, or outcome that meets all the following criteria:

- Unexpected in terms of nature, severity, or frequency given (a) the research procedures that are described in the protocol-related documents, such as the Institutional Review Board

(IRB)-approved research protocol and informed consent document; and (b) the characteristics of the participant population being studied;

- Related or possibly related to participation in the research (“possibly related” means there is a reasonable possibility that the incident, experience, or outcome may have been caused by the procedures involved in the research); and
- Suggests that the research places participants or others at a greater risk of harm (including physical, psychological, economic, or social harm) than was previously known or recognized.

8.4.2 *Unanticipated Problem Reporting*

Unanticipated problems (UPs) such as:

- Post-marketing withdrawal of a drug, device, or biologic used in a research protocol due to safety concerns.
- FDA ban of a drug, device, or biologic used in a research protocol due to safety concerns.
- Complaint of a participant when the complaint indicates unexpected risks, or the complaint cannot be resolved by the research team
- Breach of confidentiality
- Incarceration of a participant when the research was not previously approved under Subpart C and the investigator believes it is in the best interest of the subject to remain on the study
- Premature closure of a study (e.g., due safety, lack of efficacy, feasibility, financial reasons, etc.)

should be reported by the investigator to the reviewing Institutional Review Board (IRB) and to the Data Coordinating Center (DCC)/lead principal investigator (PI). The UP report will include the following information:

- Protocol identifying information: protocol title and number, PI’s name, and the IRB project number;
- A detailed description of the event, incident, experience, or outcome;
- An explanation of the basis for determining that the event, incident, experience, or outcome represents an UP;
- A description of any changes to the protocol or other corrective actions that have been taken or are proposed in response to the UP.

To satisfy the requirement for prompt reporting, UPs will be reported using the following timeline:

- UPs that are serious adverse events (SAEs) will be reported as any other SAE.

- Any other UP will be reported to the IRB and to the DCC/study sponsor the investigator becoming aware of the problem.
- All UPs should be reported to appropriate institutional officials (as required by an institution's written reporting procedures), the supporting agency head (or designee), and the Office for Human Research Protections (OHRP) after the IRB's receipt of the report of the problem from the investigator.

8.4.3 Reporting Unanticipated Problems To Participants

N/A

8.5 Device Reporting

Safety reporting for the device will be according to 21 CFR 812.150.

9 STATISTICAL CONSIDERATIONS

9.1 Statistical Hypotheses

H_0 : There is no difference between the laser group and the control group in microbial load reduction based on CFU.

H_a : There is a difference between the laser group and the control group in microbial load reduction based on CFU.

Primary endpoint: The difference in bacterial reduction between the experimental group (laser) and the comparison group (routinely used irrigation protocol) by measuring reduction in colony forming units (CFU). Friedman's and Wilcoxon signed-rank tests will be used to compare the amount of bacteria before and after treatment in both groups, with significance levels set at 5% ($P < 0.05$).

Secondary endpoints:

Measurement of pain: Following a previous published study done at the Department of Endodontics, University of Pennsylvania¹. Patients will be asked to rate the intensity of preoperative pain on a numeric rating scale (NRS) from 0 (no pain) to 10 (worst pain) before receiving root canal treatment. Along with NRS, the Wong-Baker facial grimace scale will also be presented to the patients to help them in scoring the pain. At the end of each visit, the patients will be given a survey and asked to rate the intensity of postoperative pain at 4, 24, and 48 h after the procedure. Patients will be instructed to take 1000-mg acetaminophen as needed. If acetaminophen was consumed, the patients will be asked to record the dose and time on the survey. They will be provided stamped return envelopes to mail surveys back to the Department of Endodontics (*attachment 1*).

Treatment success determined clinically and radiographically: Radiographically, Following periapical (PAI) index by Órstavík², description of radiographic findings: 1. Normal periapical structures. 2. Small changes in the bone structure. 3. Change in the bone structure with mineral loss. 4. Periodontitis with a well-defined radiolucent area. 5. Severe periodontitis with exacerbating features. Success is defined as either complete (radiographic resolution of a periapical lesion - the radiographic sign of inflammatory processes surrounding a root tip) or incomplete healing (scar tissue formation) and failure includes uncertain healing (radiographic reduction of a periapical lesion or same lesion size) or unsatisfactory healing (increase in lesion size) as determined on the radiograph. Clinically success is defined by the absence of pain, swelling, percussion sensitivity or sinus tracts. Clinical failure is defined as the persistent presence of any of the symptoms mentioned above. Treatment success/failure measured at 6 month, 1 year and 2 year follow up (\pm 7 days) post root canal filling.

9.2 Sample Size Determination

Decrease in microbial load based in CFU.

Sample size calculation, with 80% power ($\beta = 0.20$), indicated a minimum sample size of 52 teeth (26 per group) to show a 5% ($\alpha = 0.05$) difference between groups. The calculations were made in the G*Power 3.1 program.

Test: Independent t test.

Two tails.

Statistical test: Means: Wilcoxon-Mann-Whitney test (two groups).

Effect size: 0.8 (large)

$\alpha = 0.05$, $\beta = 0.20$

Attrition rate of 30% was considered, indicated a minimum sample size of 76 teeth (38 per group).

9.3 Populations for Analyses

Patients presenting to the Department of Endodontics, School of Dental Medicine, University of Pennsylvania for evaluation and routine endodontic treatment of infected, necrotic teeth with chronic apical periodontitis who meet the inclusion criteria specified above.

9.4 Statistical Analyses

9.4.1 General Approach

For descriptive statistics, categorical data will be presented as present/absent or divided into groups. Continuous data will be presented as percentages, means with standard deviations, median, range.

9.4.2 Analysis of the Primary Efficacy Endpoint(s)

Primary endpoint: The difference in bacterial reduction between the experimental group (laser) and the comparison group (routinely used irrigation protocol) by measuring reduction in colony forming units (CFU). Friedman's and Wilcoxon signed-rank tests will be used to compare the

amount of bacteria before and after treatment in both groups, with significance levels set at 5% (P < 0.05).

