The laser has been used with importance in most medical and dental specialties, especially in Endodontics in the last decade. Its properties are known in the incision of tissues, in cases of pulpotomy, and reduction of postoperative pain. Regarding the use inside the root canal, there are still some doubts about its effectiveness. Lasers, regardless of types, are individually unable to eliminate contaminations in the root canal since the root canal temperature will reach the limit to where damage to adjacent tissues and nerves occurs before bacteria are ablated¹⁷. In order for lasers to ablate all contaminants in the root canal, the absorption efficiency of laser energy at the root canal surface has to increase greatly at lower laser power without substantially raising the temperature in the root canal. Due to the high affinity of water with Erbium laser, different Erbium family lasers (Er:YAG 2940nm and Er,Cr:YSGG 2780nm) represent the cutting-edge technology for laser-activated irrigant (LAI) in Endodontics. These two wavelengths are the most appropriate for different irrigant solutions, considered safe and respecting accepted clinical parameters¹⁸.

An FDA cleared ER:Cr;YSSG laser machine (Waterlase Express™, BIOLASE®) will be tested (*clearance number: K161669, attachment 2*). This machine has different settings which are clinically suitable to be used in root canal disinfection protocols. Many studies have been published to test the efficacy of ER:Cr;YSSG laser in biofilm removal inside the root canal system¹⁹. Qualitative and quantitative *in vitro* studies showed that ER:Cr;YSSG laser activation of 4% NaOCl resulted in greater *E. faecalis* biofilm reduction within the dentinal tubules²⁰, and improved antimicrobial effect of NaOCl in comparison to syringe irrigation²¹. One blind randomized clinical trial concluded that ER:Cr;YSSG laser can achieve promising endodontic outcome, however larger sample size with longer follow-up periods are needed²². This study is to validate the method of using (Waterlase Express™, BIOLASE®) to ablate or disinfect microbe contaminants, and achieve cleaning of the root canal in association with standard endodontic procedures.

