2.3.3 Assessment of Potential Risks and Benefits

The risks or discomforts that can arise during or after any routine root canal treatment procedure apply. All subjects will receive the same standard of care disinfection protocol, with one arm receiving the additional Waterlase Express™ laser. However, this device do involve Class IV lasers that can harm eyes. Participants, providers and observers will wear appropriate laser protection eyewear (OD 3 or greater) whenever the laser is in use. Our consent forms (for routine root canal procedures and for the study) contain clinic and investigator contact information (*attachment 4 and 5*). Subjects' concerns or complaints will be reviewed routinely.

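### The primary endpoint names neither a scale nor a post-treatment sample (S2 or S3), so the stated 80% power belongs to no defined variable

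*Combined protocol and SAP*

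**What the plan says.** The null hypothesis in section 9.1 is "There is no difference between the laser group and the control group in microbial load reduction based on CFU". Section 9.4.2 says the endpoint is assessed "by measuring reduction in colony forming units (CFU", and applies Friedman's and Wilcoxon signed-rank tests to the "amount of bacteria before and after treatment in both groups". The synopsis, section 3 and section 9.4.4 repeat this definition. Section 9.2 describes the sized outcome as "Decrease in microbial load based in CFU", with "Effect size: 0.8 (large"), 80% power and a two-sided 5% level. It arrives at 26 teeth per group. It then adds "Attrition rate of 30% was considered", giving 38 per group and 76 in total.

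Sections 4.1 and 8.1 describe three canal samples at Visit 1:
- S1 is taken after initial access.
- S2 is taken after instrumentation, with NaOCl in one arm and with saline plus laser in the other.
- S3 is taken after ultrasonically activated NaOCl irrigation in all canals of both arms.

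These two sections name the independent t-test and Wilcoxon-Mann-Whitney. Section 9.4.1 mentions percentages, means and medians, but only for descriptive statistics. No section gives a rule for zero counts.

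**The concern.** Two choices that define the primary variable are left open.

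**Sample.** S2 measures the step in which the arms differ. S3 measures what remains after both arms have had the same NaOCl step. A difference at S2 that has gone by S3 supports another conclusion than one that persists. The stated aims do not settle the choice. Section 2.2 wants to "achieve cleaning of the root canal in association with standard endodontic procedures", and section 2.3.3 says "All subjects will receive the same standard of care disinfection protocol, with one arm receiving the additional" laser, which suggests the whole procedure and so S3. Sections 4.1 and 6.1.2 replace NaOCl with saline plus laser during instrumentation, which suggests S2.

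**Scale.** Raw, percent and log10 reductions are different variables, and an effect of 0.8 on one is not 0.8 on another. Section 2.2 treats an undetectable culture as the goal, so zero counts should be expected, and a log scale needs a rule for them.

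Two things follow. The 80% cannot be checked for the analysis that will be run. And the choice could be made with results in view: the investigator is unblinded (section 6.3) and vial labels carry the experimental group (sections 4.1 and 8.1).

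**Working it through.** **1. The plan's own figure.** Inputs from section 9.2: d = 0.8, two-sided alpha 0.05, power 80%. For the two-sample t-test, the non-centrality is d × √(n/2) with 2n − 2 degrees of freedom. The solution is n = 25.5, so 26 per group. At 26 the non-centrality is 0.8 × √13 = 2.88 and power is 80.7%. Attrition: 26 / 0.7 = 37.1, so 38 per group and 76 in total. Power at 38 is 93.1%. The figures reproduce. For Wilcoxon-Mann-Whitney with a normal parent, the requirement is 27 per group (78.9% power at 26).

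**2. Scale.** The documents give no means, SDs or correlations, so all of the following are assumptions. Take log-normal counts with log10 S1 mean 5, log10 S2 mean 2, both SDs 1, correlation 0.3, laser better, and d = 0.8 on log10 reduction.
- SD of log10 reduction: √(1 + 1 − 2 × 0.3) = 1.183. The shift is 0.8 × 1.183 = 0.947 log10, roughly a ninefold ratio.
- On raw counts, a log-normal mean is 10^m × exp((s × ln 10)² / 2), and the exponential factor for s = 1 is 14.17. Mean S1 is about 1,417,000 with SD about 20,000,000. Mean S2 is about 1,417 in control and about 160 with laser.
- The raw mean difference between arms is then about 1,257, against an SD of about 20,000,000. Raw reduction is almost entirely S1, and S1 precedes treatment.
- For ANCOVA on log10 S2, the residual SD is √(1 − 0.3²) = 0.954, so the working effect is 0.947 / 0.954 = 0.99.

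Simulated power at 26 per group:

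| Analysis | Power |
|---|---|
| t-test, raw reduction | about 2% |
| Wilcoxon-Mann-Whitney, raw reduction | about 5% |
| t-test, log10 reduction | about 80% |
| ANCOVA, log10 S2 on treatment and log10 S1 | about 94% |

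The loss depends on the assumptions. Three examples with laser worse and S1 and S2 close together, again with d = 0.8 on log10 reduction and 26 (38) per group:
- S1 3 (SD 0.5), S2 2.5 (SD 0.7), r = 0.3: raw Wilcoxon-Mann-Whitney 58% (75%), raw t about 36% (50%).
- S1 3 (SD 0.5), S2 3 (SD 0.7), r = 0.3: raw Wilcoxon-Mann-Whitney 76% (90%).
- S1 and S2 both 3 (SD 0.5), r = 0: raw Wilcoxon-Mann-Whitney 84% (96%), raw t 71% (86%).

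These are example scenarios, not bounds.

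**3. Sample.** Suppose 0.8 describes S2 and the shared NaOCl step leaves part of that standardised difference at S3. The share is an assumption; the power follows from the formula in step 1.

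| Share left | d at S3 | Power, 26 per group | Power, 38 per group |
|---|---|---|---|
| 75% | 0.6 | 56% | 73% |
| 50% | 0.4 | 29% | 41% |
| 25% | 0.2 | 11% | 14% |

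All samples are taken at Visit 1, so the number analysable may lie nearer 38 than 26.

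**4. Error rate.** In null simulations, one pre-specified ANCOVA rejects in 4.4 to 5.2% of trials. Taking the better of S2 and S3 on log10 with one fixed test gives about 8 to 10%. Choosing both sample and scale on the results, with the type of test still fixed, gives about 10 to 16%. These figures describe choosing on results, not any single analysis.

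**The case against.** The strongest reply is that the plan can be completed by ordinary reading. S2 is the only sample between the arm-specific step and the shared one. Friedman's test takes three or more related samples, so S1, S2 and S3 may all be meant to enter. Colony counts with no transformation mentioned read literally as raw counts. Percent and log10 reduction give identical Wilcoxon-Mann-Whitney ranks, so under that test only raw against ratio matters. The wording in sections 2.2 and 2.3.3 is background and risk discussion, not an endpoint definition.

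Part of this stands. The evidence pointing to S3 is indirect, and S2 is a reasonable guess. But if several samples enter, none is named as primary, and Friedman's test compares times within a group rather than the arms. The literal raw-count reading is the one that can lose most of the power.

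Three stronger readings are tempting, and the documents do not support them. A reader might infer that the sample size is wrong; it reproduces exactly. A reader might infer that the trial runs above 5% error; section 9.4.2 sets one 5% level, and nothing plans a choice on results. A reader might infer that raw counts always fail; step 2 gives counter-examples.

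It is also fair to object that the fix leaves two laboratory details open: plates too crowded to count at the highest dilution, and how two mesial canals become one value per tooth. Each needs a sentence of its own.

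**Conclusion.** The concern holds in this form: scale and post-treatment sample are undefined wherever the primary endpoint appears, and the effect of 0.8 is attached to no variable. That the omission exists rests on the text alone. Its size rests on assumed distributions. Power can be anywhere from about 2% to about the planned 80% depending on how the endpoint is read, and from 56% down to 11% at S3 (26 per group) if the shared step leaves between three quarters and one quarter of the S2 effect. False-positive inflation, to roughly 8 to 16%, arises only if sample or scale is chosen on results. This is more than a matter of tidiness, because the literal raw-count reading can make the primary comparison nearly uninformative, while a better analysis is available from data already planned.

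**What to change.** Before any counts are examined by arm:
- In sections 9.1, 9.2 and 9.4.2, name one primary post-treatment sample: S2 if the question is the arm-specific step, S3 if it is the whole procedure. Make the other secondary.
- Make the primary between-group analysis an ANCOVA of log10 CFU/mL at that sample, with treatment and log10 S1 as terms.
- Fix a zero-count rule. One colony from 0.25 mL plated undiluted is 1 / 0.25 = 4 CFU/mL, so half of that, 2 CFU/mL, is one option.
- Add a rank-based sensitivity analysis, such as Wilcoxon-Mann-Whitney on counts at that sample with zeros tied lowest, or a rank ANCOVA adjusted for S1.
- In section 9.2, state the sample and scale to which 0.8 refers, with the mean difference and SD behind it, and say that the 80% applies to that variable before allowing for undetectable counts.

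The cost is analysis-plan wording; the samples are already taken at Visit 1. There are two downsides. The result is reported as a ratio of geometric means, which is less familiar than a count difference. The zero rule is somewhat arbitrary, so the rank-based analysis should be reported beside it.

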9.4.3 Analysis of the Secondary Endpoint(s)

Secondary endpoint:

Measurement of pain: Following a previous published study done at the Department of Endodontics, University of Pennsylvania¹. Patients will be asked to rate the intensity of preoperative pain on a numeric rating scale (NRS) from 0 (no pain) to 10 (worst pain) before receiving root canal treatment. Along with NRS, the Wong-Baker facial grimace scale will also be presented to the patients to help them in scoring the pain. At the end of each visit, the patients will be given a survey and asked to rate the intensity of postoperative pain at 4, 24, and 48 h after the procedure. Patients will be instructed to take 1000-mg acetaminophen as needed. If acetaminophen was consumed, the patients will be asked to record the dose and time on the survey. They will be provided stamped return envelopes to mail surveys back to the Department of Endodontics (*attachment 1*).

Treatment success determined clinically and radiographically: Radiographically, Following periapical (PAI) index by Órstavík², description of radiographic findings: 1. Normal periapical structures. 2. Small changes in the bone structure. 3. Change in the bone structure with mineral loss. 4. Periodontitis with a well-defined radiolucent area. 5. Severe periodontitis with exacerbating features. Success is defined as either complete (radiographic resolution of a periapical lesion - the radiographic sign of inflammatory processes surrounding a root tip) or incomplete healing (scar tissue formation) and failure includes uncertain healing (radiographic reduction of a periapical lesion or same lesion size) or unsatisfactory healing (increase in lesion size) as determined on the radiograph. Clinically success is defined by the absence of pain, swelling, percussion sensitivity or sinus tracts. Clinical failure is defined as the persistent presence of any of the symptoms mentioned above. Treatment success/failure measured at 6 month, 1 year and 2 year follow up (\pm 7 days) post root canal filling.

